11.4. Appendix 4: Treatment States and Study Phases

11.4.1. Study Phases

- Screening Period: Day -28 to Day -1
- Treatment Period: Day 1 to Day 29/study treatment stop date
- Follow-up period: Study treatment stop date + 1 to follow-up visit date (study treatment stop date + 14 if follow-up visit date is missing)

11.4.2. Treatment States

Assessments and events will be classified according to time of occurrence relative to the start and/or stop date of the study treatment as either pre-treatment, on-treatment, or post-treatment.

11.4.2.1. Treatment States for Laboratory Data, Vital Signs, ECG Data

For laboratory data, pre-dialysis vital signs, and ECGs, treatment state will be defined as:

Treatment State	Definition
Pre-Treatment	Date ≤ Study Treatment Start Date
On-Treatment	Study Treatment Start Date < Date ≤ Study Treatment Stop Date + 1
Post-Treatment	Date > Study Treatment Stop Date + 1

NOTES:

- If the study treatment stop date is missing then any assessment after study treatment Start Date will be considered to be On-Treatment.
- Post-dialysis vital signs measured on the "Study Treatment Start Date" will be considered to be On-Treatment.

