4.2. Treatment Arms and Duration

The total duration of subject involvement is up to 10 weeks (Screening to Follow-up) as described below:

- Screening will be for at least 28 days prior to randomization. A window of ±2 days will be allowed for visits during the Screening period.
- Subjects who meet eligibility criteria will be randomized and begin dosing on Day 1. Subjects will discontinue their current ESA therapy and will be randomized to receive one of four three-times weekly doses, or placebo on a dialysis day as listed in Table 1. Examples of switching are provided in the Study Reference Manual (SRM).
 - This should be timed such that randomization (Day 1) occurs on the date that would have been the next scheduled dose of ESA (or as close as practicable).

- o For subjects with a three-times weekly dialysis schedule, Day 1 must not occur on the first dialysis session of the week (e.g., if Monday-Wednesday-Friday schedule, the study visit cannot be on Monday).
- o For subjects with a four- to five-times weekly dialysis schedule, Day 1 can be on any hemodialysis session of the week.
- The Treatment period will be for a total of 29 days. A window of ± 2 days is allowed for visits during the Treatment period.
 - At Day 29, all subjects will receive their last dose of study treatment and should not re-start ESA therapy until after the follow-up visit (Day 43).
 However, if the Investigator has a compelling clinical reason why a subject should restart ESA between Day 29 and Day 43, then ESA may be restarted prior to Day 43.
- A Follow-up visit will be scheduled to occur 14 ± 3 days after completing treatment.

Subjects will be randomized 1:1:1:1:1 to one of 5 treatment arms:

Table 1 Study Treatment Arm Descriptions

Treatment Arm	Description
А	10 mg GSK1278863 three-times weekly
В	15 mg GSK1278863 three-times weekly
С	25 mg GSK1278863 three-times weekly
D	30 mg GSK1278863 three-times weekly
Е	Placebo three-times weekly

Stopping algorithms are provided in Section 5.6.2 if Hgb values meet protocol prespecified ranges.

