 - a. For a subject who receives dialysis 3-5 times per week and starts dosing on Monday or Tuesday, the expected dose days are: 1, 3, 5, 8, 10, 12, 15, 17, 19, 22, 24, 26, and 29.
 - b. For a subject who receives dialysis 3-5 times per week and starts dosing on Wednesday or Thursday, the expected dose days are: 1, 3, 6, 8, 10, 13, 15, 17, 20, 22, 24, 27, and 29.
 - c. For a subject who receives dialysis 3-5 times per week and starts dosing on Friday or Saturday, the expected dose days are: 1, 4, 6, 8, 11, 13, 15, 18, 20, 22, 25, 27, and 29.
2. Determine the “expected cumulative number of tablets” by comparing the last dose day (last dose date – first dose date +1) with the expected dose days. For example, for a subject who received dialysis 3 times per week and started dosing on Wednesday, if the subject’s last dose day is day 7, then the expected cumulative number of tablets taken from a bottle should be 3 (because the last dose was administered before the fourth dose day); if the subject’s last dose day is day 8, then the expected cumulative number of tablets taken from a bottle should be 4 (because the last dose was administered on the fourth dose day).
3. For all other situations which is not covered in step “1” (i.e. a subject who does not receive dialysis 3-5 times per week and/or does not start dosing on Monday – Saturday), the following formula will be used to estimate the “expected cumulative number of tablets” taken from each bottle during the treatment period:

$$\text{Expected cumulative number of tablets} = \text{round}((i - 1) * 3/7, 1) + 1$$

Where “i” is the “last dose day”.

Overall compliance for a subject is categorized as follows: >0% and <80% if compliance for at least one bottle is <80%, 80% to 120% if compliance for all three bottles is between 80% and 120%, and >120% otherwise.

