7.1.2. Planned Hgb Efficacy Statistical Analyses

Primary Statistical Analyses
Endpoint(s)

 • Hgb change from baseline at Day 29
Model Specification

 • The primary endpoint is change in Hgb from baseline at Day 29. To model the dose-response relationship a three-parameter Emax model is planned, where Emax is assumed an appropriate model based on the biology and QD-dose-response modeling completed to date for GSK1278863. 
This model assumes the following form:
 $\Delta Hgb = E0 + \frac{(Emax - E0)}{1 + \left(\frac{ED50}{dose}\right)} + \epsilon$ 
Where:
 
 • ΔHgb is the change in Hgb from baseline at Day 29 • E0 is the placebo response • Emax is the maximum response

Primary Statistical Analyses											

 ED50 is the dose that attains the intermediate response, i.e. where $(E_0 + E_{max}) / 2$, is attained ϵ is a random error assumed to be normally distributed with mean zero and constant variance (σ^2) 
The observed change in Hgb from baseline at Day 29 will be used as the response variable in the Emax model. Subjects who have a Day 15 Hgb measurement but a missing Day 29 Hgb measurement will be included with a Day 29 value imputed (see Section 11.7.2.1). Any subject who prematurely discontinues dosing prior to Day 15 will be non-evaluable for the dose-response analysis.
											
Prior Distribution											

The Emax model will be fitted using Bayesian statistical methods (i.e. a posterior Emax model). Prior distributions for each of the model parameters have been based on the estimates obtained from GSK study PHI113633. This modeling provides confidence in setting prior distributions for E0, however, there is greater uncertainty in the estimation of Emax and ED50, which will be explored in sensitivity analyses with alternative (weaker) prior distributions.
											

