
Model Results Presentation
 
 As described above with Posterior Estimates, model parameters estimated from the Bayesian Emax model will be summarized through means, SD, median, MCSE/SD and equal-sided 95% credibility intervals. Median and 95% credibility intervals from Bayesian analyses and the model estimates and 95% CIs from frequentist analysis will be presented for MED, TD, and selected doses corresponding to the change of -0.25, 0.25, 0.5, 0.75 and 1 g/dL in Hgb from baseline. The Hgb dose response curve will be plotted as a line through the medians (of the predicted values of Hgb change from baseline on day 29 at a series of doses) and 95% credibility bands, and overlaid on a scatter plot of the observed data. A posterior probability distribution of predicted Hgb (g/dL) change over 29 days for each treatment group will be generated. A predictive posterior probability distribution of Hgb (g/dL) change over 29 days anticipated for a future subject, for each treatment group will be plotted. Density plots for each Emax parameter showing the prior and posterior distribution for the primary analysis overlaid with sensitivity priors analyses will be generated. A predictive posterior probability plot over the dose range to describe the probability that dose will maintain Hgb within the range of [-0.5, 0.5] g/dL after 29 days for a future subject will be generated. Dose ratios estimated by different approaches will be tabulated.

Additional Results Presentation
 
Listing of Hgb (and HemoCue Hgb data), Hgb change from baseline and Hgb derived parameters will be provided.

Analysis Datasets
 
 Unless otherwise specified, efficacy inference will be based on the ITT population using an observed case dataset, comprising of all non-missing data collected up to discontinuation of study drug and withdrawal from the trial. For dose response analysis based on ITT population, the analysis dataset comprises (1) all observed non-missing Hgb data collected up to Day 29; and (2) imputed Hgb value at Day 29 for subjects who have a Day 15 Hgb measurement but a missing Day 29 Hgb measurement.

Sensitivity and Supportive Statistical Analyses

To assess the robustness of the primary efficacy conclusions the dose-response analysis will be repeated using the sensitivity approaches described below.

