11.6. Appendix 6: Derived and Transformed Data

11.6.1. General

Multiple Measurements at One Time Point

 • Three pre-dialysis measurements and three post-dialysis measurements of SBP, DBP and HR will be recorded at each study-specified visit. Mean of the measurements will be calculated and used in any derivation of summary statistics but if listed, all data will be presented. • After window assignment, if there are two or more values within a time window, the algorithm described in Section 11.3.2 will be followed. • Subjects having both High and Low values for Normal Ranges at any post-baseline visits for safety parameters will be counted in both the High and Low categories of “Any visit post-baseline” row of related summary tables. This will also be applicable to relevant Potential Clinical Importance summary tables.
Study Day

 • Calculated as the number of days from randomisation date : 
 • Ref Date = Missing → Study Day = Missing • Ref Date < Randomisation Date → Study Day = Ref Date – Randomisation Date • Ref Date ≥ Randomisation Date → Study Day = Ref Date – (Randomisation Date) + 1
Randomization Date

 • Date subject was randomized
Treatment Start Date

 • The date of first dose of study treatment
Treatment Stop Date

 • Calculated as the date of final dose of study treatment received. If treatment stop date is missing, then, for purposes of calculating exposure, it will be imputed using the date of last visit or the recorded date of withdrawal/completion, whichever is earlier. Note that the follow-up visit date must not be used as the date of last visit or recorded date of withdrawal/completion because this date will be off-treatment.
Study Completion/Withdrawal Date

 • Date of withdrawal for subjects withdrawing (i.e., subjects who actively withdraw or are deemed lost to follow-up) from study or date of completion of study for subjects who complete the study, as documented in the eCRF. 
 • Note: Subjects who die while on study are considered as having completed the study
Time Definitions (per GSK standard principles)

 • 1 week = 7 days • 1 month = 30.4375 days • 1 year = 365.25 days

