11.7.2.1. Handling of Missing Hgb and Other Data

Element	Reporting Detail
Hgb	
 • The Hgb concentration analyzed by Quest Diagnostics is referred to as Hgb throughout this document. These data will be summarized and analyzed. If the Hgb concentration measurement is missing and a corresponding valid HemoCue Hgb concentration measurement is available, the HemoCue Hgb concentration measurement will be used for all summaries and analyses. • The dose response dataset will be based on the ITT population using an observed case dataset, comprising all non-missing data collected up to Day 29. For subjects who have a Day 15 Hgb measurement but a missing Day 29 Hgb measurement, a change from baseline at Day 29 value will be imputed using $2 * (\text{Day 15 Hgb} - \text{Baseline Hgb})$. The assumption is deemed appropriate based on phase 2a data indicating linear response over time. Any subject who prematurely

Element	Reporting Detail
	
discontinues dosing prior to Day 15 will be non-evaluable for the dose-response analysis. In general, the imputed data for the dose response analysis will not be used in summaries and figures, except for those generated specifically for dose response results. However, for descriptive summaries of Hgb over time, raw Day 29 Hgb will be summarised as well as Day 29 Hgb including imputations. The number of imputed Day 29 Hgb values will be summarized by treatment group.
 
• All other efficacy inference will be based on the ITT population using an observed case dataset.
Other Data	
• For laboratory data no imputation for missing data or premature discontinuation will be performed and the observed values will be used. The same approach applies to other assessments such as vital signs and electrocardiograms (ECGs) examination data.

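### The SAP gives two rules for the primary dose-response dataset when a subject has a Day 29 Hgb but no Day 29 dose: the body text keeps the value, the table notes do not admit it

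*SAP*

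**What the plan says.** **Treatment state.** SAP 11.4.2.1 calls a laboratory value post-treatment when "Date > Study Treatment Stop Date + 1". SAP 11.6.1 defines the stop date: "Calculated as the date of final dose of study treatment received".

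**Dosing calendars.** For Monday or Tuesday starts SAP 6.2.6 says "the expected dose days are: 1, 3, 5, 8, 10, 12, 15, 17, 19, 22, 24, 26, and 29"; for Wednesday or Thursday starts, "the expected dose days are: 1, 3, 6, 8, 10, 13, 15, 17, 20, 22, 24, 27, and 29". Friday or Saturday starts also have Day 27 as the dose before Day 29. Protocol 4.2 adds, for subjects dialysed three times weekly, that "Day 1 must not occur on the first dialysis session of the week".

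**Primary dataset, body text.** SAP 7.1.2 states: "The observed change in Hgb from baseline at Day 29 will be used as the response variable in the Emax model". Its dose-response dataset is "all observed non-missing Hgb data collected up to Day 29" plus imputed values. SAP 11.7.2.1 describes the same dataset as "comprising all non-missing data collected up to Day 29" and imputes 2 x (Day 15 - baseline) only if the Day 29 value is missing. Protocol 9.3.2 agrees. None of these sets an on-treatment condition on the Day 29 value.

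**Primary dataset, table notes (SAP 11.14.6).** Tables 2.5, 2.7, 2.8 and 2.10 take observed Hgb only if on-treatment, together with imputed Hgb. Table 2.9 takes on-treatment observed Hgb only.

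**Stopping rule.** Protocol 5.6.2 stops study drug for certain confirmed HemoCue findings, including a rise of 1.0 g/dL or more over 2 weeks. HemoCue is scheduled at Day 29, and that day's dose is given in clinic.

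**The concern.** Two programmers could build different primary datasets from this SAP. They would differ on subjects who attend Day 29 and have a valid Hgb, but are not dosed that day.

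Such a value lies within an ordinary dosing interval. The +1-day allowance is a sensible safety convention, but it is shorter than the gap between doses in a three-times-weekly regimen. If the notes are followed, a second question opens: the value is present, so the imputation rule for missing values does not clearly apply, yet the value may not be used.

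The omission need not be random. A subject whose HemoCue at Day 29 meets a stopping criterion may miss the dose for that reason, and the notes would then remove a value because of what it showed. If this is settled after unblinding, it is settled with the affected values in view.

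**Working it through.** **1. Dates.** All three calendars have 13 doses, matching the 13 expected doses in SAP 6.2.6. The fallback formula agrees: round(28 x 3/7) + 1 = 13.

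| Start day | Dose before Day 29 | Gap to Day 29 | On-treatment ends if no Day 29 dose | Day 29 Hgb |
|---|---|---|---|---|
| Mon/Tue | Day 26 | 3 days | Day 27 | post-treatment |
| Wed/Thu | Day 27 | 2 days | Day 28 | post-treatment |
| Fri/Sat | Day 27 | 2 days | Day 28 | post-treatment |

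If the Day 29 dose is given, on-treatment ends on Day 30 and the texts agree. One missed dose leaves compliance at 12/13 = 92.3%, so it does not by itself breach the 80% compliance limit for the per-protocol population.

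**2. How near the stopping rule is.** Protocol 9.2.1 uses E0 = -0.666, Emax = 5.258 and ED50 = 37.28 or 78. In the SAP's Emax model the mean change at 30 mg is:
- ED50 37.28: -0.666 + 5.924 x 30/67.28 = 1.98 g/dL
- ED50 78: -0.666 + 5.924 x 30/108 = 0.98 g/dL

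With response linear in time (the SAP's imputation assumption), the mean 2-week rise is 0.99 or 0.49 g/dL, against a threshold of 1.0.

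**3. Imputed against observed.** Let r be the Day 1-to-15 rise, R the Day 15-to-29 rise, and d = Day 1 value minus baseline. SAP 2.1 sets baseline as the mean of Week -2 and Day 1.
- Observed change = d + r + R
- Imputed change = 2(d + r)
- Imputed minus observed = d + r - R

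A subject who first meets the rise rule at Day 29 has r < 1.0 and R of at least 1.0 on HemoCue. If laboratory values agree and d = 0, the difference is negative. For r = 0.3 and R = 1.3 the change goes from +1.6 to +0.6, and the mean of a 15-subject arm moves by -1.0/15 = -0.07 g/dL. One standard error of that mean, at SD 1, is 1/sqrt(15) = 0.26.

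The sign is not guaranteed. With Week -2 10.0, Day 1 10.4, Day 15 11.3 and Day 29 12.3, baseline is 10.2, d = 0.2, r = 0.9 and R = 1.0. Observed change is 2.1 and imputed change is 2.2.

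**4. Illustrative upper cases.** Simulation of 200,000 subjects per arm with the parameters in step 2. Assumed, not in the documents: visit noise 0.3-0.5 g/dL, the share of noise common to HemoCue and laboratory, and the share of rule-meeters who miss the dose. The SD of 1.0 is the protocol's. Between 11% and 27% of the 30 mg arm first meet the rise rule at Day 29.

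| Shift in 30 mg mean (g/dL) | All rule-meeters miss the dose | 25% miss it |
|---|---|---|
| Imputed, noise fully shared | -0.12 to -0.34 | -0.03 to -0.08 |
| Imputed, half shared | -0.06 to -0.18 | -0.01 to -0.04 |
| Imputed, independent | 0.00 | 0.00 |
| Dropped | -0.02 to -0.17 | -0.01 to -0.04 |

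Among rule-meeters the imputed value exceeds the observed one in about 1-3% of cases with fully shared noise, about a quarter with half-shared noise, and half with independent noise.

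**5. Target dose.** The value is ED50 x 0.666/5.258 = 4.7 mg (ED50 37.28) or 9.9 mg (ED50 78). If all rule-meeters miss the dose:
- ED50 37.28: 4.7-6.2 mg (imputed) or 5.1-5.4 mg (dropped)
- ED50 78: 9.9-13.1 mg (imputed) or 10.8-11.9 mg (dropped)

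The largest moves, 1.5 and 3.2 mg, lie inside the half-widths of 2.86 and 5.94 in protocol Table 4. A separate linear-fit simulation, with the dose withheld for a rise of 1.0 or more or a fall of 2.0 or more, moved the target dose from 5.3 to 6.7-7.3 mg and from 10.8 to 12.9-13.6 mg. With 10% missing the dose at random it moved by about 0.1 mg.

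**The case against.** The best defence is that the body text already decides the matter. The section that defines the analysis datasets keeps the value, the imputation trigger is a missing value, and SAP 11.3.2 gives a scheduled value precedence. The note to Listing 13 bars only slotted post-treatment Hgb from change from baseline. SAP 11.14.3 describes the shells as guidance. That makes keeping the value the better reading, but no text says that the body prevails over the notes. These notes also state data rules rather than layout.

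Other points narrow the issue, and they stand:
- Table 2.27 counts subjects who are on-treatment at Day 15 and/or Day 29. It is not a clear conflict.
- SAP 8.1.2 is secondary and declares its own on-therapy dataset, so it contradicts nothing.
- Visits may move by 2 days. A Day 28 visit after a Day 27 dose is on-treatment.
- A subject who merely misses the Day 29 dose may still be a completer, and the Table 2.6 note has no explicit on-treatment limit. Only a subject stopped at Day 29 is outside the completer analysis.
- The falls and low values in the stopping criteria would remove low values, so the direction is not one-sided.

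A reader might infer that the +1-day rule is itself wrong, that imputation always pulls responders down, or that the primary result is materially biased. The documents support none of these. The rule is ordinary for safety data, the sign can reverse under the SAP's baseline, and the protocol plans a Day 29 dose for every subject.

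**Conclusion.** The inconsistency is real, concerns the primary model, and needs no assumption to establish. On the nominal calendar dates, a scheduled Day 29 Hgb without a Day 29 dose is kept by SAP 7.1.2, SAP 11.7.2.1 and protocol 9.3.2. It is not admitted by the notes to Tables 2.5 and 2.7-2.10, which leave its replacement or omission open.

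Its size is uncertain and probably modest. The number affected is unknown and may be zero, and under the body text the effect on the primary model is nil. Under the notes, subjects stopped for a Hgb rise would usually get a lower imputed than observed value if HemoCue and laboratory values move together. If their errors are independent there is no average shift from imputation. The larger shifts require every rule-meeter to miss the dose, and even these stay within the stated precision of the target dose.

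It is worth fixing because the exclusion can depend on the outcome and the choice belongs before unblinding. Confidence is high on the textual conflict and low on any particular magnitude.

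**What to change.** Before unblinding:

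1. State that the SAP 7.1.2 and 11.7.2.1 rule governs the primary model and the sensitivity fits that share its dataset. Use an observed Hgb from the Day 29 visit whether or not that day's dose was taken. Impute from Day 15 only when no Day 29 value exists.
2. Say that this includes a Day 29 visit at which drug is stopped and which the site records as Early Withdrawal. Otherwise SAP 11.3.1 would slot that value, the Listing 13 note would bar it, and the outcome-driven case would stay unresolved.
3. Remove or redefine the on-treatment condition for the Day 29 value in the notes to Tables 2.5 and 2.7-2.10.
4. For the secondary on-treatment Hgb analyses (SAP 8.1.2 and the matching summaries), count a Day 29 visit Hgb drawn within one scheduled dosing interval of the last dose, up to 3 days, as on-treatment. This is for consistency and does not correct an error. Leave the safety-laboratory and AE windows at +1 day.

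The cost is a few sentences and one derived Hgb flag, with no new data. The downside is that a few Hgb values drawn 2-3 days after the last dose count as on-treatment, and the Hgb efficacy window differs from the safety window.
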